Ethics committee approval numbered 2022/65 was received from the Düzce University Non Interventional Health Research Ethics Committee. Our study, which received project support numbered 2023.04.04.1402 from Düzce University Scientific Research Projects Coordinatorship, was designed as a prospective, observational study in the Anesthesiology and Reanimation Clinic of the Faculty of Medicine Hospital. Informed consent was obtained from all patients.

Patients over the age of 18 who underwent general anesthesia and had an American Society of Anesthesiologists (ASA) score between I-III were included in the study. Patients who had undergone or were planned to undergo head and neck surgery, who were scheduled to undergo thyroidectomy, who had congenital or acquired morphological disorders, and who had a history of difficult airways were excluded from the study.

It is reported in the literature that the rate of difficult intubation is approximately 17%. This study determined the minimum sample size required to detect a statistically significant difference (effect size= 0.1) as 273 individuals under 95% power and 5% type I error conditions. Power analysis was performed with the PASS v.15 demo program.

329 patients who met the inclusion criteria were included in the study. Following routine vital monitoring (ECG, SpO₂, NIBP) in the preoperative evaluation room, age, gender, weight, height, body mass index (BMI), Modified Mallampati score, and upper lip bite test (ULBT) values were recorded.

Anthropometric lengths were measured as described with the help of a tape measure;

1. Thyromental distance: the distance from the thyroid notch to the lower tip of the chin when the patient's head is in a neutral position
2. Neck circumference: the measurement around the entire neck with the help of a tape measure, just below the thyroid cartilage
3. Mouth opening distance: the distance between the upper and lower incisors at maximum mouth opening
4. Sternomental distance: the length from the sternal notch to the mentum when the neck is extended

The ultrasonic evaluation was performed with the 4- 15 MHz linear probe of the Esaote MayLab sevenR ultrasound in the supine position, with the head and neck in a neutral position. The distances

to the anterior neck surface were obtained by placing the linear probe in a transverse position at three different levels;

1. Minimum distance from the hyoid bone to the skin surface (DSHB) at the level of the hyoid bone

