2. Distance from the skin to the epiglottis (DSE) at the midpoint between the hyoid bone and the thyroid cartilage at the level of the thyrohyoid membrane
3. Minimum distance from the skin to the vocal cord anterior commissure (DSAC) at the level of the anterior commissure
4. Distance between the skin and the trachea (DST) 2 cm above the sternal notch, with the trachea seen transversely
5. Maximum tongue thickness in the sagittal axis under the chin with a 1- 8 MHz convex probe while the patient was in the neutral position.
6. The distance from the hyoid bone shadow to the mentum via the convex probe while the patient's neck is in extension (DSHBE) and neutral (DSHBN) positions. All USG evaluations were performed by an independent trained anesthesiologist.

Patients were induced with 2-2.5 mg/kg propofol, 1 mcg/kg fentanyl and 0.6 mg/kg rocuronium.

Mask-ventilated patients were intubated by direct laryngoscopy by an anesthesiologist with different professional experience after the count became 0 with neuromuscular monitoring using GE Healthcare's line of NMTR accessories. Cormack-Lehane score was recorded. Patients who could not be intubated were taken over by more experienced specialist physicians. Patients who could not be intubated by direct laryngoscopy by an anesthesiologist with 5 years or more experience, who used video laryngoscopy, fiberoptic bronchoscopy, and who required stylet, bougie, and cricoid pressure in addition to video laryngoscopy were evaluated as having difficult intubation.

The data obtained from the patients were subjected to various pre-processing steps to make them suitable for classification. Although there are many methods for pre-processing, the pre processing steps applied to the data set used in this study were the editing of null data, categorization of data, and feature extraction. After the completion of the null data, the textual data in the data set was converted to categorical data. Since there was little difficult intubation data in the data set, data augmentation was performed to prevent memorization in the data.

Data balancing was performed for the difficult intubation class, which was in the minority, using SMOTE (Synthetic Minority Over-Sampling Technique). SMOTE increased the samples of the minority classes and balanced the unbalanced classes.

Machine Learning Algorithms

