The data labeled with expert opinion on whether there was a difficult intubation was classified using 8 different machine learning algorithms, which are among the most widely used classification algorithms in the literature and have proven success in this field. These algorithms are; Logistic Regression (LR), Support Vector Machine (SVM), Random Forest (RF), K-Nearest Neighbors (KNN), Gaussian Naive Bayes (GNB) , CatBoost, XGBoost ve Decision Tree (DT). These algorithms were applied to the dataset, and the results were obtained.

The 15 most affecting features determined by the feature extraction method from the 30 parameters in the dataset were selected and the dataset was prepared for the classification process according to these features. In addition, different pre-processing methods, such as editing and categorizing the "null" values, were applied to the dataset. Models were created for each algorithm. The data set was evaluated in 2 groups: 80% training and 20% testing. After training and testing each model with data, the results were obtained. K-fold Cross-validation, the training data is divided into k equal parts. The divided parts are used for both training and testing. 5-Fold cross-validation was performed on the training data. This prevented overfitting of the data.

FLOW CHART

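### The classes are balanced with SMOTE and no step returns the models to the cohort's event rate, so any risk output would be inflated and the operating point is a by-product of resampling

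*Combined protocol and SAP*

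**What the plan says.** The protocol describes a study that "was designed as a prospective, observational study in the Anesthesiology and Reanimation Clinic" and reports that "329 patients who met the inclusion criteria were included in the study". Patients were not sampled by outcome, so the cohort carries its own rate of difficult intubation, subject to one relevant restriction: patients "who had a history of difficult airways were excluded from the study". That rate is not given. The only rate stated, in the SAP's opening paragraph and again in the protocol's sample-size paragraph, is a published one: "It is reported in the literature that the rate of difficult intubation is approximately 17" per cent.

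The protocol's pre-processing paragraphs, just before Machine Learning Algorithms, give the reason for augmentation: "Since there was little difficult intubation data in the data set, data augmentation was performed to prevent memorization in the data". They then name SMOTE as the method, applied to the smaller class, and state its result: "SMOTE increased the samples of the minority classes and balanced the unbalanced classes".

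Machine Learning Algorithms, printed in both the SAP and the protocol, lists eight classifiers, an 80/20 split and five-fold cross-validation inside the training part. It sums up the evaluation as "After training and testing each model with data, the results were obtained".

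The SAP part does not mention SMOTE. Neither part names a target class ratio, a cut-off, a recalibration step, a calibration check, PPV or NPV, or says whether balancing came before or after the split. The flow chart announced at the end of the protocol is not in the available text, so it is not counted either way.

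**The concern.** A model fitted where half the records are difficult intubations learns that difficult intubation is common. Used on unselected surgical patients, its scores are too high unless something converts them back. The usual 0.5 cut is then a much lower cut on the true-risk scale than it appears. This follows from the class ratio in the training data, so it applies even if SMOTE was confined to training rows.

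A second consequence is conditional. If the rows used for evaluation were balanced as well, PPV and NPV describe a population in which every second patient is difficult, and a clinician reading them would overestimate how often a warning is right.

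The stated aim is to predict difficult intubation, so both the score and the meaning of a positive call matter.

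**Working it through.** The plan gives no figure on this point to reproduce. Its minimum sample size of 273 does not enter.

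**Inputs.** From the documents: 329 patients, an 80/20 split, and a literature rate of 17%. Assumed: 1:1 balancing (the text says only that classes were balanced), an exact prior shift, a 0.5 cut, and an equal-variance binormal score with AUC 0.80. Rates of 10% and 25% are shown as a range.

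**Scale of augmentation at 17%.** 329 × 0.17 ≈ 56 difficult, leaving 273 not difficult (the match with the planned minimum is a coincidence). Full balancing adds 273 − 56 = 217 synthetic cases, and 217/273 = 79% of the difficult class is then synthetic.

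**Inflation of risk.** Balanced odds = true odds × (1 − p)/p. At 17% the factor is 0.83/0.17 = 4.88, a log-odds shift of 1.59.

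- True risk 0.17: odds 0.205 × 4.88 = 1.00, shown as 0.50.
- True risk 0.30: odds 0.429 × 4.88 = 2.09, shown as 2.09/3.09 = 0.68.
- In reverse, a shown score of 0.80: odds 4/4.88 = 0.819, a true risk of 0.819/1.819 = 0.45.

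**Predictive values.** For AUC 0.80, the separation is √2 × 0.8416 = 1.190. At the balanced 0.5 cut, sensitivity = specificity = Φ(0.595) = 0.724.

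PPV = p × sens / [p × sens + (1 − p)(1 − spec)].

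- At 50%: 0.724.
- At 17%: 0.123/(0.123 + 0.229) = 0.35.

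NPV moves the other way, from 0.72 at 50% to 0.93 at 17%.

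| Assumed event rate | Odds inflation | True risk at a score of 0.5 | PPV at that rate (AUC 0.80) |
|---|---|---|---|
| 10% | 9.0 | 10% | 0.23 |
| 17% | 4.9 | 17% | 0.35 |
| 25% | 3.0 | 25% | 0.47 |

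The 25% PPV is 0.181/(0.181 + 0.207). The AUC is itself an assumption: at 17%, an AUC of 0.70 gives PPV 0.27 (0.645 at 50%), and an AUC of 0.90 gives 0.48 (0.818 at 50%).

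**Operating point.** With AUC 0.80 and a 17% rate, the balanced 0.5 cut flags about 35% of real patients (sensitivity 0.72, specificity 0.72, PPV 0.35). A 0.5 cut on true risk flags about 6% (sensitivity 0.23, specificity 0.97, PPV 0.64). The AUC is the same in both.

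**Precision of an untouched test set.** 0.20 × 329 ≈ 66 patients, and 66 × 0.17 ≈ 11 events. For a sensitivity of 0.72, the standard error is √(0.724 × 0.276/11) = 0.135, so a 95% interval is roughly ± 0.26.

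**The case against.** A reader might infer that the models' positive calls are not valid for real patients. The documents do not support that. Balancing moves the operating point; it does not remove discrimination, and sensitivity, specificity and AUC do not depend on prevalence. If the 20% test part kept its natural mix, its PPV and NPV already apply at the cohort's rate.

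A reader might also infer that the study's PPV is known to be overstated, or that balancing preceded the split. Neither is shown. The protocol presents balancing as pre-processing of the data set before it mentions the split, but order of description is not order of execution. The PPV gap above is therefore conditional.

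Further points carry weight. The stated task is classification, and predicted risk is never named as an output. No cut-off is stated, so 0.5 is an assumption. A low effective cut may be sensible where missed cases are costly: in the illustration it finds 72% of difficult cases against 23%. SMOTE interpolates between cases, and tree, nearest-neighbour and support-vector models need not follow an exact prior shift. The 17% is not the cohort's rate, and excluding known difficult airways could change it.

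These objections limit the size and reach of the point but do not remove it. A low cut would be defensible if chosen, but the reason given for augmentation is avoiding memorisation, and no trade-off between missed and false alarms is stated. Leaving probabilities out of the output does not help, because a classifier that thresholds a score carries the same shift into its calls.

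**Conclusion.** The point holds in a limited form. The protocol balances a prospective cohort, and no stated step returns the models to the natural rate, sets a cut or commits to evaluation on real patients. Under 1:1 balancing and an approximate prior shift, any risk read from the models is inflated about 4.9-fold in odds at 17%, and a conventional 0.5 cut acts at about the event rate, so the operating point arises from resampling and not from a stated choice.

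The change in class ratio does not undermine AUC. PPV, NPV and accuracy are misleading only if the evaluation data were balanced, which cannot be settled from the text. The inflation factors are approximate and may differ between the eight algorithms. This should be corrected, but it does not make the study's discrimination results unusable.

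**What to change.** Add to the SAP, and rerun where the analysis was done otherwise:

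1. If SMOTE is kept, apply it only to training rows within each fold. Leave the validation folds and the 20% test set unaugmented.
2. Recalibrate each model's output using unaugmented training folds, by intercept correction (at 17%, subtract 1.59 from the log-odds) or Platt scaling. Pre-set the cut on the same data and state the reason for it.
3. Report sensitivity, specificity, PPV, NPV and calibration with confidence intervals, on real patients at the observed rate, and state that rate.
4. Add a fit without resampling as a comparison.
5. Do not substitute balanced class weights unless they are also recalibrated; they cause the same shift.

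No new patients are needed; the work is a short SAP addition and a rerun. The cost is in the results. PPV and F1 will look less favourable than on balanced data. With about 11 events expected among 66 test patients at 17%, the estimates will be imprecise. Recalibration also rests on few events: about 263 × 0.17 ≈ 45 in training, or 9 per fold.

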Orginal Title: Evaluation of Anthropometric and Ultrasonographic Measurements With Different Machine Learning Methods in Predicting Difficult Intubation: A Prospective Observational Study

Brief Title: Anthropometric and US-Guided Difficult Intubation Prediction With ML Models

NCT Number: NCT06904586

UPDATE DATE: 20.04.2025

ETHICS APPROVAL DATE: 18.04.2022

Statistical Analysis Plan

It is reported in the literature that the rate of difficult intubation is approximately 17% (3). This study determined the minimum sample size required to detect a statistically significant difference (effect size= 0.1) as 273 individuals under 95% power and 5% type I error conditions. Power analysis was performed with the PASS v.15 demo program.

Machine Learning Algorithms

The data labeled with expert opinion on whether there was a difficult intubation was classified using 8 different machine learning algorithms, which are among the most widely used classification algorithms in the literature and have proven success in this field. These algorithms are; Logistic Regression (LR) , Support Vector Machine (SVM) , Random Forest (RF), K-Nearest Neighbors (KNN), Gaussian Naive Bayes (GNB) , CatBoost, XGBoost ve Decision Tree (DT). These algorithms were applied to the dataset, and the results were obtained.

The 15 most affecting features determined by the feature extraction method from the 30 parameters in the dataset were selected and the dataset was prepared for the classification process according to these features. In addition, different pre-processing methods, such as editing and categorizing the "null" values, were applied to the dataset.

Models were created for each algorithm. The data set was evaluated in 2 groups: 80% training and 20% testing. After training and testing each model with data, the results were obtained. K-fold Cross-validation, the training data is divided into k equal parts. The divided parts are used for both training and testing. 5-Fold cross-validation was performed on the training data. This prevented overfitting of the data.

PROTOCOL

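### The 15 of 30 features are, as written, chosen on the whole data set rather than within the training patients and folds, so test patients can help pick the predictors

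*Combined protocol and SAP*

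**What the plan says.** The Protocol's pre-processing paragraphs treat feature extraction as preparation of the full study data: "pre processing steps applied to the data set used in this study were the editing of null data, categorization of data, and feature extraction".

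The Machine Learning Algorithms section, in the same words in the SAP and the Protocol, then reports: "The 15 most affecting features determined by the feature extraction method from the 30 parameters in the dataset were selected", and adds that "the dataset was prepared for the classification process according to these features". After that comes the division: "The data set was evaluated in 2 groups: 80% training and 20% testing". Training data are named only for the cross-validation, with an assurance attached: "5-Fold cross-validation was performed on the training data. This prevented overfitting of the data".

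The data are "classified using 8 different machine learning algorithms", so the results also serve to compare methods. Neither document names the selection method, states the order of the steps outright, or names a performance measure.

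**The concern.** A hold-out set is an independent check only if its outcomes play no part in building the model, and choosing predictors is part of building the model. Describing the chosen features as those with the most effect implies a ranking against difficult intubation. If that ranking used all 329 patients, a feature related to the outcome by chance in the test patients was more likely to be kept, and the model was then scored on those same patients.

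Cross-validation run after such a selection has the same flaw, because each held-out fold has already helped to choose the list. It cannot detect overfitting that arose in the selection step.

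Two things are at stake: performance figures that look better than new patients would give, and a comparison of algorithms that is distorted if the bias is not the same for each. The test part is small, so a few patients can carry weight.

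**Working it through.** **1. What each step is said to act on**

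| Step | Data named | Limited to training patients? |
|---|---|---|
| Null handling, categorisation, feature extraction (Protocol, pre-processing paragraphs) | study data set | No |
| Choice of 15 from 30 (SAP and Protocol, Machine Learning Algorithms) | data set | No |
| Reduction to the chosen features (same) | data set | No |
| 80/20 division (same) | data set | This step creates the training part |
| Five-fold cross-validation (same) | training data | Yes, but selection is not said to be redone in each fold |

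The authors specify training data where they mean it, and they do not do so for selection.

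**2. Size of the test part.** Inputs from the Protocol: 329 patients, literature rate 17% (the observed count is not given).
- Test patients: 0.20 × 329 = 65.8, about 66; training: 329 − 66 = 263.
- Events overall: 0.17 × 329 = 55.9, about 56.
- Events in the test part: 0.17 × 65.8 = 11.2, about 11.

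**3. Simulation of the leak.** The plan has no figure of its own to reproduce, so the size rests on assumptions. AUC is used for illustration.
- 329 patients, 56 events, stratified split 263/66.
- 30 normal predictors in five blocks of six; within-block correlation 0, 0.5 or 0.7.
- One predictor per block shifted by 0, 0.4 or 0.8 SD in patients with events. In correlated scenarios the other five are either unshifted or shifted by correlation × shift.
- Top 15 by ANOVA F statistic, chosen (a) on all 329 or (b) on the 263 training patients, with the same split and models.
- Ridge logistic regression (LR, C = 1), Gaussian naive Bayes (GNB), k-nearest neighbours (KNN, k = 5). No SMOTE.
- 800 runs in each of 12 scenarios (3 noise, 9 signal). Bias = mean test AUC under (a) − mean test AUC under (b); Monte Carlo SE at most 0.004.

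| Scenario | LR | GNB | KNN |
|---|---|---|---|
| Correlated signal (0.5–0.7) | +0.001 to +0.028 | +0.022 to +0.043 | +0.011 to +0.020 |
| Independent signal, 0.4 / 0.8 SD | +0.060 / +0.022 | +0.052 / +0.021 | +0.024 / +0.023 |
| Noise, correlation 0.5 / 0.7 | +0.051 / +0.019 | +0.057 / +0.045 | +0.012 / +0.001 |
| Independent noise | +0.097 | +0.075 | +0.028 |

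With independent noise the correct AUC is 0.5. Training-only selection gave 0.500 (LR), 0.499 (GNB) and 0.500 (KNN); whole-data selection gave 0.597, 0.574 and 0.528. The mean difference was above zero in all 12 scenarios, though KNN with noise at correlation 0.7 cannot be told from zero.

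The correlated-signal row is probably nearest to this study, because the predictors overlap: "age, gender, weight, height, body mass index (BMI), Modified Mallampati score, and upper lip bite test (ULBT) values were recorded", and several skin-to-airway depths are measured as well.

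**4. Cross-validation.** For five-fold cross-validated LR, the whole-data list was compared with selection redone in each fold. Bias: +0.087 (independent noise), +0.023 to +0.059 (independent signal), +0.002 to +0.035 (correlated signal).

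**5. Comparison of algorithms.** The order of LR and GNB reversed in 2 of the 9 signal scenarios. In one, whole-data selection gave LR 0.688 < GNB 0.708, while training-only selection gave LR 0.685 > GNB 0.670. LR gained 0.688 − 0.685 = 0.003 and GNB gained 0.708 − 0.670 = 0.038. On average 1.9 to 3.7 of the 15 features differed between the two approaches.

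**6. Second simulation.** 3,000 runs, independent predictors, ranking by |mean₁ − mean₀| / SD, logistic regression:
- no signal: 0.595 vs 0.503 (+0.092);
- 5 features at 0.3 SD: 0.678 vs 0.610 (+0.068);
- 10 features at 0.3 SD: 0.733 vs 0.678 (+0.055);
- 5 features at 0.5 SD: 0.771 vs 0.729 (+0.042).

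With no signal the bias rose to +0.112 at a 10% event rate and +0.157 at 5%.

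**The case against.** The text does not prove a leak. Order of narration is weak evidence: the Machine Learning Algorithms section reports that the algorithms were applied before it mentions selection or the split, and it mentions null handling after selection although the pre-processing paragraphs list it first. The word for the data set is used loosely throughout. The Protocol ends with a flow chart heading whose content is not visible in the text available. The selection method is unnamed, and one that ignored the outcome would leak much less.

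The likely bias is also modest. Keeping 15 of 30 is a mild filter. By the Hanley–McNeil formula, an AUC of 0.70 with 11 events and 55 non-events has Q₁ = 0.70/1.30 = 0.538, Q₂ = 2 × 0.49/1.70 = 0.576 and variance [0.21 + 10 × (0.538 − 0.49) + 54 × (0.576 − 0.49)]/(11 × 55) ≈ 0.0089, so SE ≈ 0.09. The correlated-signal bias is well below that. Finally, the simulation omits SMOTE, uses normal variables where some real ones are categorical, and covers three of the eight algorithms.

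Much of this stands as a limit on certainty and size. The code may have selected correctly; the noise scenarios are an upper illustration, not an expectation; and nothing is shown for SVM, random forest, CatBoost, XGBoost or the decision tree. It does not remove the defect. Followed as written, the plan lets test outcomes into selection, and no sentence prevents it. Sampling error does not excuse a bias that runs upward on average.

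**Conclusion.** The concern holds and should be fixed. As described, feature selection is not confined to the training patients or the folds. Under outcome-based selection on all patients, neither the hold-out nor the cross-validated result is an independent check, and the overfitting assurance is unsupported for the selection step.

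The bias in test AUC is probably small to moderate for these data (+0.001 to +0.043 across the three algorithms simulated) and larger if predictors are weak, less correlated, or events rarer than 17%. It differed among those three algorithms and could change which of two looked better.

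Confidence is medium. The conclusion rests on reading the steps as acting on the full data set and on a ranking against the outcome. The sizes rest on 56 assumed events, an assumed correlation structure, an ANOVA F filter and no SMOTE, so they show the selection leak alone.

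**What to change.** State in the SAP and the Protocol that:
- the data are split first;
- the 15 features are selected on the 80% training data only, by a named method;
- selection is repeated within each cross-validation fold;
- the frozen training-set list is applied to the test patients.

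If null completion estimates values from the data, fit it on training data in the same way; fixed-rule null handling and fixed category coding need no change. Remove or qualify the sentence on overfitting. If selection was in fact confined to the training data, say so instead. Reporting how often each feature is chosen across folds is optional.

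The cost is two or three sentences. A re-run on existing data is needed only if selection used all patients, and no new patients are required. The performance figures may become slightly less favourable, and about 2 to 4 of the 15 features may change.

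### Could the Cormack-Lehane score, seen only at laryngoscopy, have entered the models as a predictor because the 30 candidate parameters are not listed?

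*Combined protocol and SAP*

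**What the plan says.** Both Machine Learning Algorithms sections carry the same sentence: "The 15 most affecting features determined by the feature extraction method from the 30 parameters in the dataset were selected". Neither lists the 30, names the ranking method or criterion, or sets a time limit on candidates.

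The title gives the aim: "Evaluation of Anthropometric and Ultrasonographic Measurements With Different Machine Learning Methods in Predicting Difficult Intubation".

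The protocol then describes data collection in order:

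- In the preoperative room, "age, gender, weight, height, body mass index (BMI), Modified Mallampati score, and upper lip bite test (ULBT) values were recorded".
- Next, "Anthropometric lengths were measured as described with the help of a tape measure", followed by four lengths.
- Then a numbered list of ultrasound distances and tongue thickness.
- After that come induction, neuromuscular block and direct laryngoscopy, where "Cormack-Lehane score was recorded".
- The rule for difficult intubation follows, beginning "Patients who could not be intubated by direct laryngoscopy by an anesthesiologist with 5 years or more experience, who used video laryngoscopy, fiberoptic bronchoscopy" and going on to adjuncts. It does not mention the Cormack-Lehane score.

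The next paragraph says "The data obtained from the patients were subjected to various pre-processing steps to make them suitable for classification". The steps it names are handling of missing values, categorisation and feature extraction. It adds that "the textual data in the data set was converted to categorical data".

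**The concern.** The study asks whether difficult intubation can be foreseen from measurements taken beforehand. A predictor seen only once the laryngoscope is in place cannot serve that purpose. The candidate pool is described only by its size. The Cormack-Lehane score is recorded but given no role, and no pre-processing step is said to remove variables recorded after induction. Read literally, the score could be a candidate.

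If it were, it would plausibly rank high, because it is graded during the same laryngoscopy in which the outcome arises. It could then displace an anatomical measurement from the 15. All eight models are built on those 15, so their reported performance could not be reached before induction. Neither the 80/20 split nor the 5-fold cross-validation would reveal this, since the same column would be present in training and test data.

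The count sharpens the suspicion, because the documents name clearly fewer than 30 preoperative variables.

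**Working it through.** The only figure to reproduce is the pool of 30. It cannot be rebuilt from the named variables, so the question is what the shortfall shows.

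**Inputs (protocol, measurement paragraphs).** I take the tape-measure and ultrasound items as pre-induction, as the order of description implies.

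- Bedside: age, gender, weight, height, BMI, Mallampati, upper lip bite test = 7
- Tape measure: thyromental distance, neck circumference, mouth opening, sternomental distance = 4
- Ultrasound: DSHB, DSE, DSAC, DST, tongue thickness, DSHBE, DSHBN = 7
- ASA class, named as an eligibility item = 1
- ECG, SpO₂, NIBP, named only as routine monitoring; treating them as dataset variables is an assumption = 3

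**Step 1. Named preoperative items.** 7 + 4 + 7 = 18. With ASA, 19. With the monitored items, 22.

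**Step 2. Unidentified candidates.** 30 − 18 = 12 (12/30 = 40%), 30 − 19 = 11 (37%), or 30 − 22 = 8 (27%). These are columns that the documents do not itemise. They are not a count of columns recorded after induction.

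**Step 3. Can preoperative items alone reach 30?** The protocol documents a conversion of text to categories, so coded columns are possible. Assume that gender, Mallampati, lip bite test and ASA are expanded to one column per level, with 2, 4, 3 and 3 levels (assumed). The other 19 − 4 = 15 items stay as they are. Then 15 + (2 + 4 + 3 + 3) = 27, and the three monitored items bring it to 30. This is one possible route, not evidence that it was taken. It shows that the shortfall does not point to laryngoscopy items.

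**Step 4. Can preoperative items alone fill the 15 places?** Yes, since 18 ≥ 15. The number of laryngoscopy items needed is 0.

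**Step 5. Does the title set the limit?** Not strictly. Tape-measure and ultrasound items number 4 + 7 = 11, or 14 with weight, height and BMI, which is below 15. On the items described, between 15 − 14 = 1 and 15 − 11 = 4 kept features must be something else or derived. Age, gender, Mallampati and the lip bite test are four such items, all recorded preoperatively.

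**Step 6. Largest role of the score.** At most 1/30 = 3% of candidates and 1/15 = 7% of kept features. This is a share of columns, not of predictive performance. The effect on performance cannot be calculated from the documents and may be zero.

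**The case for a change.** The strongest opposing case is textual. The pre-processing sentence refers to the data obtained from patients and comes directly after the intubation paragraph, so the Cormack-Lehane score falls within its plain meaning. The title cannot be the operative limit (step 5). Listing the 30 parameters with the time of each would cost almost nothing and would settle whether the results are usable before induction. The Machine Learning Algorithms section also attributes the label to expert judgement. If the experts had the score in view, using it as a predictor would be circular as well as late.

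Part of this stands. The list and the timing limit are not written down, and a reader cannot confirm from the documents that every candidate was preoperative.

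The rest depends on a premise that the documents do not supply: that the score was one of the 30. Being recorded for a patient is not the same as being a candidate parameter. The protocol sets out the preoperative measurements as one block, and the score appears later, beside the outcome rule, where it reads as descriptive or outcome-side information. The circularity argument needs the same premise. So does any worry about device or adjunct use, since no passage makes those items dataset columns. Even the assumption that features were ranked by their effect on the label is inference, because the criterion is not named.

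**Conclusion.** The concern does not call for a change. The plan omits the list of 30 candidates and does not say when each was recorded. It contains no instruction that, when followed, brings a laryngoscopy finding into the models. Analysts predicting difficult intubation from anthropometric and ultrasound measurements would ordinarily draw candidates from the preoperative block, which is large enough to fill all 15 places.

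The 8 to 12 unidentified columns measure how much the text leaves unlisted, not how much leakage there is. The one laryngoscopy finding recorded by name accounts for at most 1 of 30 candidates and 1 of 15 kept features, and nothing shows that it accounts for any.

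This rests on two assumptions: that the tape-measure and ultrasound items were taken before induction, as the order of the protocol implies, and that the score served as descriptive or outcome-side information. The documents neither confirm nor contradict the second. A study report would normally list the features used, and that list would show whether the second assumption holds.
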